8.3. Events or Outcomes Qualifying as AEs or SAEs

8.3.1. Clinical laboratory parameters

Abnormal laboratory findings (e.g., clinical chemistry, hematology) or other abnormal assessments (e.g. vital signs) that are judged by the investigator as **clinically significant** will be recorded as AEs or SAEs if they meet the definitions of sections 8.1 and 8.2 respectively. Clinically significant abnormal laboratory findings or other abnormal assessments that are detected during the study or are present at informed consent and significantly worsen during the study will be reported as AEs or SAEs. Clinically significant abnormal laboratory findings or other abnormal assessments that are associated with the disease being studied, and are present at the start of the study but do not worsen, will **not** be reported as AEs or SAEs. However, if these findings or assessments are judged by the investigator to be more severe than expected considering the subject's condition, then they may be reported as AEs or SAEs.

8.3.2. Pregnancy report

Subjects who become pregnant at any time will be immediately withdrawn from participation in the study. All appropriate withdrawal assessments may be performed at the discretion of the investigator.

The investigator will collect pregnancy information on any woman subject or partner of a male subject, who becomes pregnant and their partner while participating in this study. The investigator will record pregnancy information and submit it to ABIVAX or its designee within 24 hours after knowledge of a subject's or partner's pregnancy. The subject or partner will also be followed to determine the outcome of the pregnancy, be it full-term or prematurely terminated. Information on the status of the mother and child will be forwarded to ABIVAX or its designee. Follow-up will normally end 6 to 8 weeks following the estimated delivery date.

While pregnancy itself is not considered to be an AE or SAE, any pregnancy complication or elective termination of a pregnancy for medical reasons will be recorded as an SAE. A spontaneous abortion is always considered to be an SAE and will be reported as such.

The time period for collecting pregnancy information is identical to the time period for collecting AEs, as stated in Section 8.4, Time Period, Frequency, and Method of Detecting AEs and SAEs. Pregnancy information is collected from the signing of informed consent to 4 weeks after the last dose.

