 - o Total serum creatinine ≤ 1.3 x ULN (upper limit of normal);
 - o Creatinine clearance > 50 mL min-1 by the Cockcroft-Gault equation within 60 days of entry;

- Total serum bilirubin < 1.5 x ULN;
- o Alkaline phosphatase, AST (SGOT) and ALT (SGPT) < 1.5 x ULN;
- Subjects should be able and willing to comply with study visits and procedures as per protocol;
- Subjects should understand, sign and date the written voluntary informed consent form at the screening visit prior to any protocol-specific procedures being performed;
- Subjects should be affiliated to a social security regimen;
- Females and males receiving the study treatment and their partners must agree to use a highly effective contraceptive method during the study and for 3 months after end of study or early termination. Contraception should be in place at least 2 weeks prior to study participation. Women must be surgically sterile or if of childbearing potential must use a highly effective contraceptive method. Women of childbearing potential (WOCBP) will enter the study after confirmed menstrual period and a negative pregnancy test. Highly effective methods of contraception include: true abstinence, intrauterine device (IUD) or hormonal contraception associated with inhibition of ovulation, intrauterine hormone releasing system, bilateral tubal occlusion, vasectomized partner. True abstinence is defined when this is in line with the preferred and usual lifestyle of the subject. In each case of delayed menstrual period (over one month between menstruations) confirmation of absence of pregnancy is required. This recommendation also applies to WOCBP with infrequent or irregular menstrual cycle.

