7. SUBJECT COMPLETION AND WITHDRAWAL

7.1. Subject Completion

Treatment with ABX464/Placebo shall continue until Day 56 visit, except if a subject fulfils a premature discontinuation criterion (defined below). After Day 56, subjects are willing to carry on the study treatment will be able to take part in an open-label study (ABX464-102).

In any other case, the subjects will exit the study (EoS) and will be treated according to the standard of care. The ABX464-102 follow-up study is a separate clinical protocol subject to health authorities and ethics committee approvals.

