8.4. Time Period, and Frequency of Detecting AEs and SAEs

All AEs and SAEs occurring from the time a subject consents to participate in the study until 4 weeks after he or she has completed or discontinued the investigational product must be recorded in the subject's eCRF.

Importantly, SAEs will have to be reported, either by email or by Fax, to SIMBEC ORION within 24 hours of awareness of an SAE.

SIMBEC ORION

[contact]

[contact]

Legislative guidance requires also reporting any **related** SAEs to be reported after the subject finished the study if the investigator becomes aware of them.

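### About 10 of the roughly 14 weeks after last dose in which contraception is required fall outside mandatory pregnancy collection

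*Protocol*

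**What the plan says.** Protocol section 4.2.1 makes eligibility depend on subjects and their partners agreeing to a highly effective "contraceptive method during the study and for 3 months after end of study or early termination". It adds: "Contraception should be in place at least 2 weeks prior to study participation".

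Protocol section 8.3.2 governs pregnancy reporting. The investigator submits a pregnancy in a subject, or in a male subject's partner, within 24 hours of learning of it, and mother and child are followed to outcome. Two time limits appear there:

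- The duty is described for a woman subject or partner "who becomes pregnant and their partner while participating in this study".
- The closing paragraph equates the pregnancy period with the adverse-event period and says: "Pregnancy information is collected from the signing of informed consent to 4 weeks after the last dose".

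The adverse-event period in section 8.4 runs from consent "until 4 weeks after he or she has completed or discontinued the investigational product must be recorded". On treatment length, section 7.1 says: "Treatment with ABX464/Placebo shall continue until Day 56 visit". The last scheduled pregnancy test is on Day 56 (section 5.3.2), and no visit is scheduled after Day 63. The SAP (section 11.4.2) only lists pregnancy data.

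**The concern.** The protocol asks subjects to avoid conception for 3 months after the study but closes its pregnancy collection 4 weeks after the last dose. A pregnancy arising between those dates would breach the contraception commitment. Yet it would fall outside the period in which the investigator must record it, send it within 24 hours and follow it to outcome. No section explains why the two end points differ.

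The primary objective is safety, and about 20 subjects are to receive active drug, so even one pregnancy after exposure would be informative. Subjects who do not enter ABX464-102 leave for standard of care, and the documents name no other study protocol that would capture the event. With no test or visit late in the period, detection depends on the subject reporting and on the site knowing that the report is wanted.

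**Working it through.** **Inputs**

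| Item | Value | Source (Protocol) |
|---|---|---|
| Screening | Day -14 | 5.1 |
| Last dose | Day 56 | 7.1 |
| End-of-study visit | Day 63 ± 2 | 5.1, 5.2.6 |
| Contraception ends | 3 months after end of study | 4.2.1 |
| Pregnancy collection ends | 4 weeks after last dose | 8.3.2 |
| Length of 3 months | 91 days; 90 to 92 tested | assumption; not defined |

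**The plan's own figure.** Participation from Day -14 to Day 63 is (14 + 63)/7 = 11.0 weeks, which reproduces the 11 weeks in section 3.2.

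**Gap for a completer**

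- Collection ends: 56 + 28 = Day 84.
- Contraception ends: 63 + 91 = Day 154.
- Gap: 154 - 84 = 70 days (10 weeks).
- Contraception after last dose: 154 - 56 = 98 days (14 weeks).
- Share of that period uncovered: 70/98 = 71%.

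**Range.** The gap equals the length of 3 months, plus the days from last dose to end of study, minus 28. The smallest case takes end of study as Day 56 and 3 months as 90 days: 90 + 0 - 28 = 62. The largest takes Day 65 and 92 days: 92 + 9 - 28 = 73. The post-dose share runs from 62/90 = 69% to 73/101 = 72%.

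**Share of the whole contraception period.** From first dose, 70/154 = 45%. From screening, 70/168 = 42%. Adding the 2 weeks required before participation lowers it to 70/182 = 38%.

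**Early discontinuation.** With the end-of-study visit 7 days after last dose, the gap is again 7 + 91 - 28 = 70 days. The share from first dose reaches one half when the last dose is on Day 42, since 70/(42 + 98) = 50%, and exceeds it only for earlier last doses.

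**Two end points inside 8.3.2.** If collection covers only pregnancies during participation, and participation ends at Day 63, the uncovered stretch is 154 - 63 = 91 days rather than 70.

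**Routes beyond week 4**

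- Section 8.1 allows the post-treatment period to be extended if incomplete elimination is strongly suspected. Section 5.3.10 gives the long-lived metabolite a half-life of 90 to 110 h. Four weeks is 672 h, so 672/110 = 6.1 to 672/90 = 7.5 half-lives will have passed. The trigger would seldom be met.
- Section 8.4 asks for related SAEs to be reported after the study if the investigator learns of them. Section 8.3.2 treats spontaneous abortion, pregnancy complications and medically indicated termination as SAEs, and section 8.2 adds congenital anomaly. These outcomes therefore have a route, conditional on relatedness and awareness.
- Section 8.3.2 says that pregnancy itself is neither an AE nor an SAE. An uncomplicated pregnancy in the gap therefore triggers neither route.

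**The case against.** The two periods may differ by design. Five half-lives of the metabolite are 5 × 90 = 450 h to 5 × 110 = 550 h, or about 19 to 23 days, inside the 28-day window. A contraception period that carries a margin beyond the reporting period is not in itself a contradiction. This stands in part: 4 weeks is not arbitrary on the protocol's own figures. But the protocol does not give that reason, and clearance would not explain why pregnancies are left uncollected in months for which the protocol still asks that they be prevented.

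Three stronger readings are tempting, and the documents do not support them.

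- A reader might infer that most of the contraception period is uncovered. That is true only of the part after last dose; over the whole period the share is below one half for a completer.
- A reader might infer that later pregnancies go unreported altogether. Related serious outcomes known to the investigator must still be reported, and section 8.1 allows an extension. What is missing is a duty to record and follow a pregnancy as such.
- A reader might take the 3 months as a risk window declared by the protocol. It states a contraception requirement and does not use that term.

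The second end point in 8.3.2 also depends on what participation means. Section 3.1.1 mentions a one-month follow-up, which would bring the two limits close together. Section 3.2's 11 weeks and the visit schedule do not include it, so the wording still needs settling.

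Finally, consent pages are not available, so subjects may already be told to report later pregnancies. ABX464-102 is not available either, and the number of subjects who will not roll over is not stated.

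**Conclusion.** The mismatch is real and unreconciled. About 70 days (range 62 to 73), or 10 of the roughly 14 weeks after last dose in which contraception is required, lie outside mandatory pregnancy collection. Section 8.3.2 also gives two end points for that collection. The routes past 4 weeks are conditional or discretionary, and neither requires an uncomplicated pregnancy in the gap to be recorded or followed to outcome.

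The size rests on 3 months being about 91 days and on dosing and end-of-study visits near Days 56 and 63. The number of subjects affected cannot be derived. This is a modest gap in safety capture, worth closing because closing it is cheap; it does not bear on power, alpha or the primary analysis. Nothing here says how long contraception should last.

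**What to change.** Reconcile sections 4.2.1, 8.3.2 and 8.4:

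1. In 8.3.2, separate the pregnancy window from the adverse-event window. Run it from informed consent to the end of whatever contraception period 4.2.1 states, for subjects and for partners of male subjects.
2. Remove the limit to pregnancies during participation, so that 8.3.2 has a single end point.
3. Add to the end-of-study visit a reminder to report a pregnancy in that period, if the consent form does not already cover it.
4. State that ABX464-102 takes over collection for subjects who roll over.

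On the present wording, collection would end at about Day 154 instead of Day 84. The cost is a short wording change, a reminder at an existing visit and a few late reports to handle after the last visit. No visit, test or analysis is added.

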8.4. Time Period, and Frequency of Detecting AEs and SAEs

All AEs and SAEs occurring from the time a subject consents to participate in the study until 4 weeks after he or she has completed or discontinued the investigational product must be recorded in the subject's eCRF.

Importantly, SAEs will have to be reported, either by email or by Fax, to SIMBEC ORION within 24 hours of awareness of an SAE.

SIMBEC ORION

[contact]

[contact]

Legislative guidance requires also reporting any **related** SAEs to be reported after the subject finished the study if the investigator becomes aware of them.

8.5. Recording AEs and SAEs

Severity of AEs will be assessed according to CTC-AE Classification Version 4.0.

Subjects will be asked to report all AEs as part of the procedures performed at each study visit. The site personnel will document all AEs in the subject's medical record. All AEs subsequently must be recorded in the appropriate eCRF sections.

The following points must be recorded for each event:

- A description of the event in medical terms, not as reported by the subject;
- · Date of onset (start date);
- Date of resolution (stop date);
- The time of onset with respect to administering the investigational product;
- The severity of the sign/symptom or clinically significant abnormal laboratory value according to CTC-AE Classification;
- The causal relationship between the investigational product and the occurrence of each AE. This
 will be assessed by each investigator using clinical judgment. Alternative causes, such as natural
 history of the underlying diseases, concomitant medications, other risk factors and the temporal
 relationship of the event to the investigational product will have to be considered. The causality of
 all AEs should be assessed by the investigator with the following question: Is there a reasonable
 possibility that the AE may have been caused by the investigational product? And answered "NO"
 (if not related) and "YES" (if related);
- Action taken regarding the investigational product:
 - o No action;
 - o Temporary discontinuation;
 - Permanent discontinuation;
 - Subject's outcome:
 - Recovered without sequelae / resolved without sequelae;
 - Recovered with sequelae / resolved with sequelae;
 - o Recovering/Resolving;
 - o On-going;
 - o Fatal (for SAEs only).

If in any one subject, the same AE occurs on several occasions, the AE in question must be documented and assessed anew each time.

8.6. Reporting of SAEs to ABIVAX or its designee

Throughout the study, the reporting of SAEs to the Sponsor or its designee will be done through the SAE forms.

It is the investigator's responsibility to ensure that the SAE report is submitted to SIMBEC ORION within 24 hours after knowledge of the event(s). The SAE forms or paper report forms should be completed as thoroughly as possible, with all the available details of the event and signed by the investigator or designee. An assessment of causality should always be provided at the time of the initial report. If the investigator or designee does not have all information regarding the SAE, he/she should not wait to receive additional information before completing the form and notifying SIMBEC ORION.

Additional or follow-up information relating to the initial SAE report, will be requested, if necessary. Again, this information is to be completed and submitted through the SAE forms within 24 hours of receipt of the information.

In the rare occasion when the facsimile equipment does not work and in the absence of, the investigator should notify SIMBEC ORION by telephone within the given timeframe, and send a copy of the SAE report form by email.

8.7. Reporting of SAEs to Regulatory Authorities

ABIVAX has a legal responsibility to notify, as appropriate, both the local regulatory authorities and other regulatory agencies about the safety of the investigational product. It is therefore important that the investigator notifies promptly ABIVAX or designee of any SAEs, in order for legal obligations and ethical responsibilities towards other subjects to be met.

In addition, the investigator or designee, will comply with the local regulatory requirements (when applicable) in reporting of SAEs to the ethics committee and, if required, to the relevant government authority.

Safety reports on adverse events that are serious AND unexpected AND associated with the investigational product are prepared according to ABIVAX's policy and applicable regulations and are forwarded to the investigators. These reports are filed with the investigator brochure or other appropriate study documentation. It is the Sponsor or its designee and/or investigator's responsibility to notify the IRB or IEC of these reports, if applicable according to local requirements.

9. DATA ANALYSIS AND STATISTICAL CONSIDERATIONS

A summary of the principal features of the statistical analysis of the data will be described here, in the statistical section of the protocol. A more technical and detailed elaboration of the principal features stated in the protocol will be given in the first version of the statistical analysis plan (SAP).

Any amendments to the SAP will be clearly documented and signed prior to the final database lock including justifications and details of their potential impact on the interpretation of the study results.

9.1. Statistical and Analytical Plans

No interim analysis is planned.

The study analysis will be performed following database lock upon the completion of the last subject or upon its early discontinuation whichever occurs first.

9.1.1. Protocol deviations

Protocol deviations will be reviewed and classed as major or minor during the blind-review meeting. Major protocol deviations are defined as deviations liable to bias the evaluation of the main efficacy endpoint. The following deviations will be considered as major (non-exhaustive list):

- Non compliance with the inclusion or exclusion criteria;
- Non compliance with the study treatment;
- Intake of prohibited medication;
- · Noncompliance with time window.

9.1.2. Definition of study analysis sets

The following datasets will be defined and used for the analyses:

- The Safety dataset (SAF population) is defined as those subjects included in the study, who have received at least one dose of the study treatment.
- The Full Analysis dataset (FAS population) is defined as those subjects included in the study, who have received at least one dose of the study treatment, and who have at least one baseline data.
- The **Per Protocol dataset (PP population)** is defined as those subjects of the FAS population without any major protocol deviation.

9.1.3. Subjects/Subjects disposition

The number and the percentages of subjects enrolled and included in each of the populations will be tabulated. The reason for subject exclusions from each of the populations will also be listed. In addition, the number of discontinued subjects with their reason for discontinuation will be tabulated.

9.1.4. Demographic and other baseline characteristics

Demographics and other baseline characteristics will be summarized by treatment arm. This analysis will be conducted on the FAS population.

9.1.5. Treatment compliance

Number of dose intakes will be presented on the FAS population.

9.2. Efficacy Analysis

Analysis of efficacy data will be carried out in the Full Analysis Set in which subjects who prematurely terminate the study will be considered failures.

The primary efficacy endpoint of the study, the rate of subjects responding to treatment. This response rate will be compared in subjects who received ABX464 or placebo by stratified likelihood ratio chi-square test on a 10% one-sided level.

In addition, descriptive statistics will be presented by treatment arm for all secondary efficacy variables for each measurement timepoints separately for the two study groups.

These statistics include:

- Continuous variables: mean, standard deviation, minimum and maximum, stratified 95% confidence intervals, median and quartiles will be presented.
- Categorical variables: counts, rates and stratified 95% confidence intervals for the rates will be calculated.

In addition to descriptive statistics, the following analyses will also be carried out for the variables indicated below:

- Kaplan-Meier estimates and plots will be presented for time to UC worsening after week 8.
- Mixed model analysis of covariance will be conducted for the following measurements:
 - O The change from screening in IL-22 expression levels in serum and rectal/sigmoidal tissue at week 8,
 - O The change from baseline in microRNA-124 levels in whole blood (PAXgene®) and in tissue (RNA later) at week 4 and week 8,
 - O The change from baseline in fecal calprotectin levels at week 4 and week 8,
 - O The change from screening in the histopathology/infiltrate (rectal/sigmoidal biopsies) assessed by the Geboes score at week 8,

In this model, treatments and stratum will be fixed effects, subjects will be random effect and baseline values of the respective measurements will be covariates. Other explanatory variables will also be allowed to be included in the model. In order to normalize eventual skewed distributions transformation of the data will also be considered. Study groups will be compared within this model framework. All p-values will be interpreted in a descriptive manner.

9.2.1. Pharmacokinetics

A total of 10 blood samples per subject will be collected for PK purpose.

Individual plasma concentrations of ABX464, NGlcABX464, Hydroxyl ABX464 glucuronide, will be presented by treatment and time points. Descriptive statistics for the plasma concentrations will be presented as number of available data (N), mean, standard deviation (SD) and will be calculated if at least 2/3 of the plasma values per time-point are above LOQ (i.e. $N \ge 10$ if 15 subjects are available for a given group). For descriptive statistics calculations, BLQ concentrations below the limit of quantification will be set to zero (0) if they are reported before the first quantifiable sample or considered as missing data if they are reported after the first quantifiable data

Then, the following PK parameters will be derived for ABX464 and NGIcABX464 for each subject:

 C_{max} , t_{max} : the maximum plasma concentration (C_{max}) and the time taken to reach C_{max} (t_{max}) will be obtained directly from the concentration-time data.

AUC $_{0-\tau}$: the area under the concentration-time curve from time zero to the time of dosing interval τ (12 h postdose for ABX464 and NGlcABX464). If no concentration can be measured at this time point, AUCO-last (from time zero to the last quantifiable concentration) will be calculated. Both parameters will be presented independently. For both parameters, a linear trapezoidal method will be used.

Individual derived PK parameters will be presented by treatment and day of PK assessment when appropriate. Descriptive statistics of the PK parameters will be presented as N, mean, SD, median, minimum (Min), maximum (Max) values, and geometric mean (GM).

In the tables of individual PK parameters, all the deviations from planned analysis will be mentioned by flagging the abnormal results.

Possible exclusion of flagged PK parameters could be performed if, in the judgment of the pharmacokineticist, they are deemed not to be "pharmacokinetically relevant". Exclusion of PK parameters will be discussed in the PK results section. If data are excluded from the PK dataset, all subsequent statistical analyses will be performed twice, once using the complete available PK dataset and once using the final PK dataset as defined by the pharmacokineticist. Study conclusion will be based on the final dataset as defined by the pharmacokineticist.

For each compound, plasma concentration vs. time curves will be presented on a log-linear scale:

- mean plots showing the data of both treatments (administration alone and co-administration with ABX464);
- by subject plots with the treatments on separate plots (spaghetti plots).

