3. INVESTIGATIONAL PLAN

3.1. Study design

3.1.1. Design and methodology

This Phase IIa study is an 8-week, double-blind, placebo-controlled, randomized study aimed at evaluating the safety and the efficacy of ABX464 given once a day (o.d) at 50 mg in subjects with moderate to severe Active Ulcerative Colitis who have failed or are intolerant to immunomodulators, Anti-TNF α , vedolizumab and/or corticosteroids followed by a one-month follow-up period.

Eligible subjects will be randomized according to a 2/1 ratio in two different groups of treatments according to the following study design.

Upon screening visit (D-14), eligible subjects will be checked for eligibility.

Subject eligibility will be confirmed by the medical staff based of the endoscopy central reading and on the laboratory results performed at screening visit. If eligibility is confirmed, then the subject will be randomized using the eCRF.

At Day 0, study drug (ABX464 or its matching placebo) will be added on top of this background therapy for the next 56 days. ABX464 or its matching placebo will be given once a day at 50 mg.

For subjects receiving oral corticosteroids during the study treatment period, tapering of steroids should start at week 4 at a rate of prednisone or prednisone equivalent 5 mg/week for 4 weeks to discontinuation. However, this study procedure is left to the Investigator's discretion.

The dose of 50 mg of the study drug has been selected based on the reassuring safety data accumulated on the 50 mg o.d. from previous studies and the high exposure in ABX464-NGluc (active metabolite) at this dose.

Eligible subjects will be randomized according to a 2/1 ratio in two different groups of treatments.

Randomization will be stratified according to the following factors: concomitant treatment with corticosteroids and previous TNF antagonist exposure.

Randomized subjects will be seen at the investigational site every week during the first month of treatment and then every two weeks during the second month. Flexible sigmoidoscopy with rectal and/or sigmoidal biopsies will be performed again at week 8.

The DSMB will meet after every 3 subjects are recruited in order to review on a regular basis the safety profile of this dose level and to recommend, if appropriate, the continuation of the study.

The sample size in this Proof of Concept study is 20 subjects receiving ABX464 and 10 subjects receiving Placebo (i.e. a total of 30 subjects).

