5. STUDY ASSESSMENTS AND PROCEDURES

5.1. Study Flow Chart

A detailed study flow chart (with all assessments) is displayed hereafter.

			Study Treatment Period								
	D-14	Randomization	D0	D7	D14	D21	D28	D42	D56	D63- EOS	
Time Window	±3 days			±2 days	±2 days	±2 days	±2 days	±4 days	±4 days	±2 days	
Obtained Inform Consent	X										
Check of IN/EX Criteria	Х	X									
Physical Examination	X		Х	X	X	X	X	X	Χ	X	
Body Weight (kg)	Х		X	X	X	X	Х	Х	X	X	
Height Measurement (cm)	X										
Medical History and Concomitant Medications	Х			-							
Vital signs	X		X	X	X	X	X	X	X	X	
ECG (12 lead)	X		X				X		X	Х	
Randomization		X		1							
Blood Pregnancy test (wocse)	X		X	1			X		X		
Hematology + Blochemistry	Х		X	X	Х		Χ		X	Х	
Mayo score (Total or Partial)	X		X	X	X	Х	X	X	X.	X	
Faecal calprotectin			X				X		Х	X	
Rectal microbiota	X						 	1	X		
Sigmoldoscopy	X		 					1	Х		
SF-38 (Questionnaire)			Х			ļ	X]	X		
ABX464/placebo treatment dispensation and subject diary review			×				X				
Blood samples drug pK			X,				Χ·				
Samples for miRNA (Paxgene tubes)			Х				х		X		
Adverse Events recording		I	X	X	l X	X	Х	X	X	 	

^{*} Applicable to the first 9 subjects randomized / PK predose, 0.5, 1, 1.5, 2, 2.5, 3, 4, 8 and 12 post-dose

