5.3.10. Pharmacokinetics

The main objective of the PK analysis is to evaluate potential PK specificities of ABX464 in subjects suffering from active UC.

ABX464 was shown to have a very short $t_{1/2}$ (1 to 2 h), so steady-state is virtually reached at the second administration, while NGlcABX464 has a $t_{1/2}$ of 90 to 110 h, meaning that steady-state is reached after 19 to 22 days of administration.

PK analysis will be performed in the first 9 subjects enrolled in this study at Week 0 and Week 4. A first blood sample (reference) will be collected on the first day of treatment before any drug administration then blood samples will be collected for PK purpose at, 0.5, 1, 1.5, 2, 2.5, 3, 4, 8 and 12 post-dose samples

A total of 10 blood samples per subject will be collected for PK purpose and sent to ATLANBIO for Bioanalyses.

Study code: ABX464-101

Blood samples for determination of ABX464, NGlcABX464, Hydroxyl ABX464 glucuronide and/ will be collected from all subjects using direct venipuncture or an indwelling catheter.

Then, the following PK parameters will be derived for ABX464 and NGlcABX464 for each subject:

- C_{max}, t_{max}: the maximum plasma concentration (C_{max}) and the time taken to reach C_{max} (t_{max}) will be obtained directly from the concentration-time data.
- AUC_{0-τ}: the area under the concentration-time curve from time zero to the time of dosing interval τ (12 h post-dose for ABX464 and NGIcABX464). If no concentration can be measured at this time point, AUC_{0-last} (from time zero to the last quantifiable concentration) will be calculated. Both parameters will be presented independently. For both parameters, a linear trapezoidal method will be used.

Moreover, evaluation of steady-state will be made by visual inspection of the pre-dose concentration measurement collected over the study duration.

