11.4. Randomization

Randomization will be centrally managed by block of 3 subjects (2 ABX464/1 placebo). It will be performed via the eCRF. The bottle numbers to be used for a specific subject will be assigned according to a pre-defined randomization list by SODIA. This information will be provided to the site by fax or by email.

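### The PK conclusion rests on a dataset that may be trimmed by undefined judgment, so an unusual but valid value could be left out of it

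*Protocol*

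**What the plan says.** Protocol 9.2.1 sets out a sequence for the derived PK parameters.

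- In the tables of individual parameters, "all the deviations from planned analysis will be mentioned by flagging the abnormal results".
- A flagged parameter may then be removed: "Possible exclusion of flagged PK parameters could be performed if, in the judgment of the pharmacokineticist", it is considered not relevant in pharmacokinetic terms. That notion is not defined, and no numerical rule or list of causes is given.
- If anything is removed, every later analysis is run on the complete dataset and again on the final one, and the exclusions are discussed in the PK results section.
- The final dataset decides: "Study conclusion will be based on the final dataset as defined by the pharmacokineticist".

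The aim in Protocol 5.3.10 is to "evaluate potential PK specificities of ABX464 in subjects suffering from active UC". The same section fixes the size: "PK analysis will be performed in the first 9 subjects enrolled in this study at Week 0 and Week 4".

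SAP 4.3 assigns PK to the sponsor and excludes its methods from the SAP. SAP 10.1 has general conventions for PK summaries but no exclusion rule. The blind data review in SAP 9.4 does not mention PK exclusions.

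**The concern.** This is a stated rule, not only a missing detail: where the two datasets differ, the plan has already chosen the trimmed one. The criterion for trimming is one specialist's judgment. The flag starts from deviations from the planned analysis, but the text speaks of abnormal results and does not require that a documented failure (of dosing, sampling or assay) explain the abnormality.

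That fits poorly with the aim. If ABX464 behaves differently in active UC, one way it could show is as an unusually high or low Cmax or AUC in some subjects. A rule that lets such a value be set aside, and draws the conclusion from the rest, could pull the summary towards the unremarkable and make between-subject variability look smaller. With about six subjects on active drug, each value carries weight.

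**Working it through.** **Is there a figure to reproduce?** No. The documents give no variability for any PK parameter and no expected effect of an exclusion. What follows is an illustration under stated assumptions.

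**Number of active PK subjects.**
- PK sampling is "Applicable to the first 9 subjects randomized" (Protocol 5.1).
- Protocol 11.4: "Randomization will be centrally managed by block of 3 subjects (2 ABX464/1 placebo").
- Expected active count: 9 × 2/3 = 6.
- Protocol 3.1.1: "Randomization will be stratified according to the following factors: concomitant treatment with corticosteroids and previous TNF antagonist exposure". If each factor has two levels there are four strata. Simulating blocks of 3 within four equally likely strata gives 4 to 8 active subjects among the first nine, and 5 to 7 in about 96% of runs. With a single unstratified list it is exactly 6.

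**Effect of removing one value.** With n values of mean m, removing x leaves a mean of (n·m − x)/(n − 1). The relative fall in the mean is therefore (x/m − 1)/(n − 1). As an example, let one of six values be twice the mean of the other five (set to 1). The full mean is (5 + 2)/6 = 1.167, and removal lowers it to 1, a fall of 0.167/1.167 = 14.3%.

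**Average effect.** Assumptions: lognormal values, n = 6, between-subject CV 40%, 60% or 80%, and 200,000 simulated samples per setting.

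| Assumed CV | Highest dropped: arithmetic mean | Highest dropped: SD | Highest dropped: geometric mean | Lowest dropped: arithmetic mean | Random value dropped: absolute change in arithmetic mean |
|---|---|---|---|---|---|
| 40% | −11.1% | −27% | −9.2% | +8.2% | 5.5% |
| 60% | −16.5% | −31% | −13.0% | +10.8% | 7.8% |
| 80% | −21.2% | −35% | −16.1% | +12.6% | 9.7% |

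**Cross-check.** For normal data the expected highest of six lies 1.267 SD above the mean, so the fall is about 1.267 × CV / 5: 10.1% at CV 40%, 15.2% at 60% and 20.3% at 80%. This is close to the first column.

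**Spread.** These are averages, not bounds. With the highest value dropped, the 5th to 95th percentile for a single trial is 4.4% to 21.0% at CV 40% and 7.9% to 42.0% at CV 80%. With five active subjects the average fall for CV 40% to 80% is 12.4% to 23.2%; with seven it is 10.1% to 19.7%.

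**The case against.** The case for leaving the text alone has several parts.

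- **Flags concern deviations from planned analysis.** They can be read as mainly procedural, and the plan nowhere says a value is flagged just for being high or low. This stands in part: the sentence is ambiguous, but nothing limits exclusion to procedural causes.
- **Trimming cannot be hidden.** Both datasets are analysed, exclusions are discussed, individual parameters are tabulated with their flags, by-subject curves are plotted, and median, minimum, maximum and geometric mean are reported. This stands. A reader might infer that a disease effect could vanish from the report; with these outputs it could not.
- **Timing.** A reader might infer that exclusions are chosen after the values, or even the treatment codes, are known. Working from derived and flagged parameters makes the first plausible, but the protocol states neither the timing nor the blinding of the decision.
- **Consequence.** PK is a secondary objective, summarised descriptively in nine subjects, with no PK hypothesis test and no comparator without UC. One might read the word study in the deciding sentence as covering the whole trial. The sentence sits in the PK section, and the primary safety and efficacy analyses do not use this dataset.
- **Rules may exist elsewhere.** The sponsor handles PK outside the SAP, so criteria may be set in another document. That cannot be settled from these two. It would not change the choice of deciding dataset that the protocol makes.

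**Conclusion.** The point holds in a limited form. Protocol 9.2.1 bases the PK conclusion on a post-exclusion dataset defined by an unstated criterion, and neither document confines exclusion to causes independent of the value. An unusual but valid result could therefore be left out of the conclusion, although finding such results is part of the PK aim. The plan's safeguards make this visible; they do not change which dataset decides.

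The size is illustrative only. It depends on an assumed lognormal shape, about six active subjects, an assumed CV of 40% to 80%, and the removal of an extreme value. Quoting any of these percentages as a property of this trial would go beyond the documents. A random exclusion, or reliance on the geometric mean, gives smaller shifts than dropping the highest value does to the arithmetic mean. The trial's primary safety and efficacy conclusions are not affected.

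**What to change.** Amend Protocol 9.2.1, or the sponsor's PK analysis document, in three ways.

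1. Base the PK conclusion on all available PK parameters except those excluded for documented reasons that do not depend on the value itself, for example a dose not taken, a sampling-time failure or an assay failure.
2. Fix the list of reasons before the PK parameters are reviewed. Tying it only to formal unblinding is weaker, because drug concentrations themselves separate active from placebo subjects.
3. Report any further exclusion based on judgment only as a sensitivity analysis, keeping the discussion of exclusions already planned.

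This needs no more subjects or samples, and the plan already provides for parallel analyses. The cost is a short list to agree in advance and, possibly, a more variable main summary. If both kinds of exclusion occur and the complete dataset is still reported, one further run of the descriptive tables is needed.
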